5.2. Determination of Sample Size

5.2.1. Clinical Protocol RHCD

Sample size of this study is based on the regulatory requirements from the European Medicine's Agency Paediatric Investigation Plan for ixekizumab. The regulatory requirements for the number of subjects in each treatment group were: (1) at least 170 randomized subjects (at least 90 to ixekizumab, at least 25 to etanercept, and at least 55 to placebo); and (2) at least 30% of subjects from the EU.

In the main protocol RHCD, approximately 165 subjects will be randomized in a 2:1 ratio to receive ixekizumab (110 subjects) or placebo (55 subjects) during the Double-Blind Treatment Period. The study will have >99% power to test the superiority of ixekizumab to placebo for PASI 75 and for sPGA (0,1) at Week 12, based on the 2-sided Fisher's exact test at a significance level of 0.05. The following assumptions were used for the power calculations for both sPGA (0,1) and PASI 75 responses rates, based on ixekizumab clinical studies in adult subjects with moderate-to-severe Ps efficacy data (Griffiths et al. 2015; Gordon et al. 2016): 80% response for ixekizumab and 10% response for placebo for both PASI 75 and sPGA (0,1).

5.2.2. Protocol Addendum RHCD(2)

During the Double-Blind Treatment Period, approximately 75 subjects with severe Ps from etanercept-approved countries will be randomized to ixekizumab (30 subjects), etanercept (30 subjects), and placebo (15 subjects) with 2:2:1 ratio.

Study RHCD(2) will have approximately 85% power to test the superiority of ixekizumab to etanercept for sPGA (0,1) and at least a 75% improvement from baseline in PASI score (PASI 75) at Week 12, based on the 2-sided Fisher's exact test at significance level of 0.05. The study will have approximately 45% power to test the superiority of etanercept to placebo for PASI 75 at Week 12, based on the 2-sided Fisher's exact test at significance level of 0.05. The following assumptions were used for the power calculations for both sPGA (0,1) and PASI 75 response rates, based on ixekizumab clinical studies in adult subjects with moderate-to-severe Ps efficacy data (Griffiths et al. 2015; Gordon et al. 2016): 80% responders for ixekizumab, 40% responders for etanercept, and 10% for placebo.

During the Double-Blind, Randomized Withdrawal Period (Period 4), approximately 40 subjects from EU countries will be re-randomized to ixekizumab (20 subjects) and placebo (20 subjects) with a 1:1 ratio. The response criterion for re-randomization is sPGA (0,1) at Week 60. The study will have approximately 95% power to test the superiority of ixekizumab to placebo in time to relapse, based on the 2-sided log-rank test at significance level of 0.05. The following assumptions were used for the power calculations: 20% relapse for ixekizumab; and 85% relapse for placebo. Relapse rates were estimated, based on ixekizumab clinical studies in adult subjects with moderate-to-severe Ps efficacy data (Griffiths et al. 2015; Gordon et al. 2016).

5.3. Method of Assignment to Treatment

Assignment to treatment groups will be determined by a computer-generated random sequence using an interactive web-response system (IWRS). The IWRS will be used to assign cartons containing double-blind study drug to each subject. Study site personnel will confirm that they have located the correct carton by entering a confirmation number into the IWRS.

5.3.1. Clinical Protocol RHCD

Subjects who meet all enrollment criteria at Visit 1 and Visit 2 will be randomized in a 2:1 ratio to double-blind treatment with ixekizumab or placebo at Week 0 (Visit 2).

To achieve between-group comparability for region, the randomization will be stratified by region (United States/Canada, European countries, and the rest of the world).

During the Maintenance and Extension periods, all subjects will receive open-label treatment with ixekizumab.

5.3.2. Protocol Addendum RHCD(2)

Subjects from countries where etanercept is approved for severe pediatric Ps treatment only who meet all criteria for enrollment at Visit 1 and Visit 2 will be randomized to double-blind treatment at Week 0 (Visit 2) in a 2:2:1 ratio to ixekizumab, etanercept, or placebo.

Subjects who meet response criteria (sPGA 0,1) from EU countries will enter the Double-Blind Randomized Withdrawal Period and will be re-randomized to double-blind treatment at Week 60 (Visit 19) in a 1:1 ratio to ixekizumab or placebo. Subjects who are re-randomized to ixekizumab will receive ixekizumab 20, 40, or 80 mg every 4 weeks (Q4W) according to their weight at the time of re-randomization. Subjects from EU countries who relapse (sPGA ≥ 2) during the Double-Blind Randomized Withdrawal Period will receive open-label treatment with ixekizumab according to their weight at the time of relapse.

6. A Priori Statistical Methods

6.1. General Considerations

Statistical analysis of this study will be the responsibility of Eli Lilly and Company (hereafter, Lilly, or its designee). The statistical analyses will be performed using SAS[®] Version 9.2 or higher.

Continuous data will be summarized in terms of the number of observations, mean, standard deviation (SD), minimum, median, and maximum. The minimum and maximum will be reported to the same number of decimal places as the raw data recorded in the database. The mean and median will be reported to 1 more decimal place than the raw data recorded in the database. The SD will be reported to 2 more decimal places than the raw data recorded in the database. In general, the maximum number of decimal places reported shall be 4 for any summary statistic.

Categorical data will be summarized in terms of the number of patients in the Analysis Population, the number of patients providing data at the relevant time point, frequency counts, and the percentages corresponding to the appropriate method. Percentages will be presented to 1 decimal place. Percentages will not be presented for zero counts.

All confidence intervals (CIs) and statistical tests will be 2-sided unless, otherwise, specified. P-values which are greater than or equal to (\geq) 0.001, and less than or equal to (\leq) 0.999, will be presented to 3 decimal places. All other p-values which are less than 0.001 will be presented as <0.001 , while p-values greater than 0.999 will be presented as >0.999 . Confidence intervals will be presented to 1 more decimal place than the raw data.

Age, gender, and race will be reported on all by-patient listings unless, otherwise, specified. Gender will be abbreviated as follows: female (F); and male (M). Race will be abbreviated as follows: American Indian or Alaska Native (AI), Asian (AS), Black or African American (BL), Native Hawaiian or other Pacific Islander (NH), White (WH), and Multiple (MU).

6.1.1. Analysis Population

Table RHCD.6.1 provides the definitions for each analysis population for specific treatment periods. Table RHCD.6.2 summarizes the treatment groups and comparisons for each study period and analysis population.

Unless, otherwise, specified, efficacy and health-outcome analyses will be conducted for the Intent-to-treat (ITT) Population (per the main study) in Double-Blind Treatment Period (Period 2). In addition, the co-primary endpoints will be analyzed using the per-protocol set (PPS).

Select efficacy analyses will be conducted on the ITT Population-Etanercept Approved Countries (per Protocol Addendum[2]) in Double-Blind Treatment Period (Period 2).

Safety analyses for the Double-Blind Treatment Period (Period 2) will be conducted on the Safety Population. There are 2 safety populations: Safety Population (per the main study); and Safety Population-Etanercept Approved Countries (per Protocol Addendum[2]).

Unless, otherwise, specified, the efficacy and safety analyses for the Double-Blind, Randomized Withdrawal Period will be conducted on the Double-Blind, Randomized Withdrawal Period Population (per Protocol Addendum[2]).

Unless, otherwise, specified, during the Combined Treatment Periods (Periods 2, 3, and 4), efficacy and health-outcome analysis will be conducted on the ixekizumab Efficacy Primary Population.

Safety analyses during the Combined Treatment Periods (Periods 2, 3, and 4) will be conducted on the All Ixekizumab Safety Population

Unless, otherwise, specified, during Combined Treatment Periods 3 and 4, efficacy analysis will be conducted on the Ixekizumab Efficacy Secondary Population.

Safety analyses for the Post-Treatment Follow-Up Period (Period 5) will be conducted on the Follow-Up Population.

Table RHCD.6.1. Analysis Populations

Population	Period	Description
Intent-to-Treat (ITT) Population (per main study)	Double-Blind Treatment Period (Period 2)	All randomized subjects, even if the subject does not take the assigned treatment, does not receive the correct treatment, or, otherwise, does not follow the protocol. Unless, otherwise, specified, efficacy and health-outcome analyses will be conducted on the ITT Population during Double-Blind Treatment Period (Period 2). Subjects will be analyzed according to the treatment to which they were assigned.
Intent-to-Treat (ITT) – Etanercept Approved Countries (per Protocol Addendum[2])	Double-Blind Treatment Period (Period 2)	All randomized subjects per Protocol Addendum(2) in etanercept-approved countries (that is, subjects with severe psoriasis in countries where etanercept is used as a reference arm), even if the subject does not take the assigned treatment, does not receive the correct treatment, or, otherwise, does not follow the protocol. Subjects will be analyzed according to the treatment to which they were assigned.
Per-Protocol Set (per main study)	Double-Blind Treatment Period (Period 2)	All randomized subjects who do not have significant protocol violations (refer to Section 6.16). Subjects will be analyzed according to the treatment to which they were assigned. .
Safety Population (per main study)	Double-Blind Treatment Period (Period 2)	All randomized subjects who take at least 1 dose of double-blind study treatment. Subjects will be analyzed according to the treatment to which they were assigned.

Population	Period	Description
Safety Population – Etanercept-Approved Countries (per Protocol Addendum[2])	Double-Blind Treatment Period (Period 2) per Protocol Addendum(2)	All randomized subjects in Protocol Addendum(2) in etanercept countries who take at least 1 dose of double-blind study treatment per Protocol Addendum(2). Subjects will be analyzed according to the treatment to which they were assigned.
Double-Blind, Randomized Withdrawal Period Population	Randomized-Withdrawal Period (Period 4) per Protocol Addendum(2)	All re-randomized patients (that is, subjects from countries in the EU who were re-randomized at Week 60) who received at least 1 dose of study treatment during Double-Blind, Randomized Withdrawal Period.
Ixekizumab Efficacy Primary Population	Combined Treatment Periods (Periods 2, 3, and 4)	All subjects randomized to ixekizumab at Week 0 (Visit 2) and who received ixekizumab throughout their study participations. The following subjects are not included in this analysis population: (1) patients randomized to etanercept or placebo at Week 0; and (2) patients who are re-randomized to placebo during Period 4 per Protocol Addendum(2).
Ixekizumab Efficacy Secondary Population	Combined Treatment Periods 3 and 4	Patients initially randomized to placebo or etanercept who switch to ixekizumab during Period 3. The following data is not included in this analysis population: (1) patients initially randomized ixekizumab; (2) Period 4 data for patients re-randomized to placebo at Week 60.
All Ixekizumab Safety Population	Combined Treatment Periods.	All subjects who have at least 1 dose of ixekizumab, including patients in main protocol and Protocol Addendum(2).
Follow-Up Population	Post-Treatment Follow-Up Period (Period 5)	Safety analyses for Post-Treatment Follow-Up Period will be conducted on the Follow-Up Population, defined as all randomized subjects who received at least 1 dose of study treatment and have entered the Post-Treatment Follow-Up Period. Patients will be analyzed according to the last treatment they received before entering Period 5.

Abbreviations: EU = European Union.

Table RHCD.6.2. Treatment Groups and Comparisons for Each Study Period and Analysis Population

Study Period	Analysis Population	Treatment Group	Abbreviation	Comparison
Double-Blind Treatment Period (Period 2)	Intent-to-Treat Population; Per-Protocol Set; Safety Population	Ixekizumab Q4W	IXEQ4W	IXEQ4W vs. PBO
		Etanercept Q1W	ETN	IXEQ4W vs. ETN
		Placebo Q4W	PBO	ETN vs. PBO
Randomized-Withdrawal Period (Period 4)	Double-Blind, Randomized Withdrawal Period Population	Ixekizumab Q4W	IXEQ4W	IXEQ4W vs. PBO
		Placebo Q4W	PBO	
Combined Treatment Periods (Period 2, 3, 4)	Ixekizumab Efficacy Primary Population, All Ixekizumab Safety Population	Ixekizumab Q4W	IXEQ4W	NA
Combined Treatment Periods 3 and 4	Ixekizumab Secondary Primary Population	Placebo Q4W/ixekizumab Q4W	PBO/IXE	NA
		Etanercept Q4W/ixekizumab Q4W	ETN/IXE	
Post-Treatment Follow-Up Period (Period 5)	Follow-Up Population	Ixekizumab Q4W	IXEQ4W	No comparison
		Etanercept	ETN	
		Placebo Q4W	PBO	

Abbreviations: ETN = etanercept; IXE = ixekizumab; NA = not applicable; PBO = placebo; Q1W = every week; Q4W = every 4 weeks; vs. = versus.

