
To assess the relationship between exposure and efficacy and exposure and immunogenicity
	
 • Model parameters for the exposure-response relationship between ixekizumab serum trough concentrations and efficacy endpoints (for example, sPGA, PASI) at Week 12

Objectives	Endpoints
	
 • Serum trough concentrations for ixekizumab antibody titer subgroups
To assess the safety of ixekizumab	
 • To evaluate the safety of ixekizumab, including but not limited to: infections; injection-site reactions; B-, T-, and NK-cell levels; WBC count; RBC count; and laboratory values (hematology and chemistry [including ALT and AST]) during the course of the study
To demonstrate normal growth and pubertal progression in children treated with ixekizumab during the course of the study	
 • Weight, height, and BMI data will be merged to the Centers for Disease Control and Prevention standard growth data by age and gender to compare subjects' growth with normal values • Shift table for Tanner stage from maximum baseline to maximum postbaseline by gender
To evaluate the genital involvement of the subjects per the questionnaire Binary Questions on Psoriasis Location	
 • Proportion of subjects achieving no psoriasis presence in each psoriasis location
To evaluate the patient's global assessment of disease severity	
 • Proportion of subjects achieving patient's global assessment of disease severity 0 or 1
To evaluate the effect of ixekizumab on maintenance of efficacy and health outcomes during the open-label maintenance period and extension period.	
 • Proportion of subjects achieving PASI 90 • Proportion of subjects achieving sPGA (0) • Proportion of subjects achieving PASI 100 • Proportion of subjects achieving PASI 75 • Proportion of subjects achieving sPGA (0,1) • Improvement ≥ 4 for subjects who had a baseline Itch NRS score ≥ 4

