- a Randomization will be stratified by region (United States/Canada, EU countries, and rest of the world) and by etanercept approval status: 1) Subjects with severe pediatric Ps (PASI ≥ 20 or sPGA ≥ 4) who are from countries where etanercept is approved for the treatment of severe pediatric Ps will be randomized to ixekizumab, etanercept, or placebo in a 2:2:1 ratio. 2) Per the main protocol, all other subjects (including those with moderate-to-severe Ps [PASI ≥ 12 and sPGA ≥ 3] from countries where etanercept is not approved for the treatment of severe pediatric Ps, and subjects with moderate pediatric Ps [12 \leq PASI < 20 and sPGA = 3] in countries where etanercept is approved for the treatment of severe pediatric Ps) will be randomized to either ixekizumab or placebo in a 2:1 ratio.
- b At Visit 2, randomization will occur according to the following weight groups: 1) < 25 kg: randomization to ixekizumab 20 mg, receiving a starting dose of 40 mg; 2) 25 kg to 50 kg: randomization to ixekizumab 40 mg, receiving a starting dose of 80 mg; 3) > 50 kg: randomization to 80 mg, receiving a starting dose of 160 mg. A staggered approach to enrollment by weight group will be implemented, with subjects aged > 12 years and weighing > 50 kg enrolling initially to the study. After an initial safety analysis of the first 12 weeks of treatment of 15 subjects weighing > 50 kg, and if no safety concern is identified, subjects will start to enroll in the 25- to 50-kg group. Once data for Week 12 for approximately 15 subjects in the 25- to 50-kg group is gathered, an interim analysis of PK, safety, and efficacy data for all subjects in the study at that point will be performed to confirm doses for future subjects in the study. Once confirmed, all weight groups will be open for enrollment.
- c Subjects receiving ixekizumab 20 mg or 40 mg will receive 1 SC injection of ixekizumab at Week 0 (Visit 2) and 1 SC injection of ixekizumab Q4W at Weeks 4 and 8. Subjects receiving ixekizumab 80 mg will receive 2 SC injections of ixekizumab at Week 0 (Visit 2) and 1 SC injection of ixekizumab Q4W at Weeks 4 and 8.
- d Subjects receiving placebo for ixekizumab 20 mg or 40 mg will receive 1 SC injection of placebo at Week 0 (Visit 2) and 1 SC injection of placebo Q4W at Weeks 4 and 8. Subjects receiving placebo for ixekizumab 80 mg will receive 2 SC injections of placebo at Week 0 (Visit 2) and 1 SC injection of placebo Q4W at Weeks 4 and 8.

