6.1.3.3. Combined Treatment Periods

Data for the combined treatment periods will be summarized using descriptive statistics.

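### The Ixekizumab Efficacy Primary Population drops Week 60 responders rerandomized to placebo together with their Week 0–60 data, which biases the Week 60 sPGA (0,1) rate low

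*SAP*

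**What the plan says.** SAP 6.1.1, Table RHCD.6.1, treats the same event in two ways in adjacent rows.

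- **Ixekizumab Efficacy Primary Population (Periods 2, 3 and 4).** Subjects randomized to ixekizumab at Week 0 who stayed on it for as long as they took part. The listed exclusions are of subjects, and the second is "patients who are re-randomized to placebo during Period 4 per Protocol Addendum(2").
- **Ixekizumab Efficacy Secondary Population (Periods 3 and 4).** The listed exclusions are of data, and the second is "Period 4 data for patients re-randomized to placebo at Week 60".

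Eligibility for rerandomization is in SAP 5.3.2: "Subjects who meet response criteria (sPGA 0,1) from EU countries will enter the Double-Blind Randomized Withdrawal Period". EU nonresponders and all non-EU subjects continue on open-label ixekizumab.

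The Primary Population is the default for long-term efficacy. SAP 6.1.1 gives the general rule, subject to any exception stated elsewhere: "during the Combined Treatment Periods (Periods 2, 3, and 4), efficacy and health-outcome analysis will be conducted on the ixekizumab Efficacy Primary Population". Table RHCD.6.4 summarizes sPGA (0,1), sPGA (0) and PASI 75/90/100 in it at every postbaseline visit of Periods 2 to 4, which includes Week 60. SAP 6.1.3.3 makes these summaries descriptive: "Data for the combined treatment periods will be summarized using descriptive statistics". SAP 6.11.4, however, places the Week 24 and Week 48 summaries of the same endpoints on the ITT Population.

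**The concern.** A subject is removed by the second exclusion only after being an EU sPGA (0,1) responder at Week 60 and then being assigned placebo. Everything recorded for that subject up to Week 60 was in the Week 0 ixekizumab arm, yet it leaves the summary. EU nonresponders are never exposed to this removal and all stay. Membership of the set therefore depends on the endpoint being summarized.

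This population serves the Table RHCD.4.1 objective "To evaluate the effect of ixekizumab on maintenance of efficacy and health outcomes during the open-label maintenance period and extension period". A rate described as that of the ixekizumab arm would differ from the full-arm rate because of a later assignment that cannot have affected response up to Week 60. In addition, Table RHCD.6.4 and SAP 6.11.4 could yield two different Week 24 and Week 48 rates for the same arm.

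**Working it through.** **The plan's own figure.** The documents give no Week 60 response rate. The related stated figure is about 95% power for the withdrawal comparison (SAP 5.2.2), with 20 per arm, relapse of 20% versus 85%, and a 2-sided log-rank test at 0.05. Hazard ratio = ln(0.80)/ln(0.15) = 0.118. Expected events = 20 × 0.20 + 20 × 0.85 = 21. Freedman power = Φ(√21 × (1 - 0.118)/(1 + 0.118) - 1.96) = 0.951. The figure reproduces, so 20 subjects on placebo is a sound planning number.

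**Direction.** Take N subjects, R Week 60 responders and k responders removed. The reported rate is (R - k)/(N - k), which is below R/N whenever k > 0 and R < N. No assumption is needed.

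**Inputs for size.**
- N = 110 randomized to ixekizumab (SAP 5.2.1).
- 20 assigned placebo: "approximately 40 subjects from EU countries will be re-randomized to ixekizumab (20 subjects) and placebo (20 subjects") (SAP 5.2.2).
- Share of those 20 who began on ixekizumab: not given. Severe subjects in etanercept-approved countries "will be randomized to ixekizumab, etanercept, or placebo in a 2:2:1 ratio" (footnote a to Figure RHCD.5.2), a share of 2/5. All others are randomized 2:1, a share of 2/3. Assuming similar Week 60 response across original arms, k lies between 20 × 2/5 = 8 and 20 × 2/3 = 13.3.
- Week 60 response p = 80%. This is the Week 12 design value; its use at Week 60 is an assumption.

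**Result at N = 110, R = 88.**

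| k | Reported rate | Shift (points) |
|---|---|---|
| 8 | 80/102 = 78.4% | -1.6 |
| 11 | 77/99 = 77.8% | -2.2 |
| 13 | 75/97 = 77.3% | -2.7 |
| 20 (upper bound) | 68/90 = 75.6% | -4.4 |

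At k = 11 the shift is -4.4 for p = 60%, -3.3 for 70% and -1.1 for 90%. The standard error of 80% at N = 110 is √(0.8 × 0.2/110) = 3.8 points.

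**Second route, from the EU share.** If a fraction f of the arm is from the EU and half of its responders go to placebo, the expected rate is approximately (p - fp/2)/(1 - fp/2). At the 30% minimum in SAP 5.2.1 and p = 80%, this is 0.68/0.88 = 77.3%, with 110 × 0.3 × 0.8/2 = 13.2 removed. A 20,000-run simulation gave 80.0% for the full set and 77.3% after exclusion. At f = 50% the rate is 0.60/0.80 = 75.0%. Within the EU stratum alone (f = 1), 80% becomes 0.4/0.6 = 66.7%.

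**Other visits.** Let a and b be the response rates at another visit among Week 60 responders and nonresponders. The shift is (a - b) times the Week 60 shift. With a = 0.90 and b = 0.40 (assumed), it is 0.5 × (-1.6) = -0.8 to 0.5 × (-2.7) = -1.3 points. It is zero if a = b.

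**The case against.** The strongest case on the other side is that little depends on this output. It is descriptive, carries no comparison in Table RHCD.6.2, and is labelled other secondary or exploratory. The central shift is below one standard error and goes against the sponsor's drug. Week 60 is not a named efficacy time point in Table RHCD.4.1. The named ones, Weeks 24 and 48, are placed on ITT by SAP 6.11.4, which can be read as overriding the default. The population can also be read as a deliberate continuous-treatment cohort with fixed membership. Finally, response only makes a subject eligible, and the removal itself is by random assignment.

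The points on importance stand and limit the weight of the finding. The others do not remove it. A continuous-treatment cohort needs only the records after rerandomization excluded. The assignment is random among responders, but nonresponders never face it, so the retained set keeps all EU nonresponders and about half of EU responders. The Week 24 and 48 override leaves Week 60 and Period 4 uncovered, and Table RHCD.6.4 still lists every postbaseline visit.

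Two cautions on the numbers also stand. Varying N from 90 to 140 and p from 70% to 90% with k fixed at 8 to 13 gives -0.6 to -5.1 points, but the ends of that range combine inputs that do not fit well together, because k itself depends on N, p and the EU share. The EU-stratum figure is illustrative and not a planned output, since efficacy subgroups are confined to Period 2.

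**Conclusion.** The point holds: the definition is wrong as written. The downward bias in the Week 60 sPGA (0,1) rate is certain in direction whenever anyone is removed and not everyone responds. On planned numbers it is about 2 to 3 points, and about 5 if half the arm is from the EU. The size rests on an assumed 80% Week 60 rate, on an assumed ixekizumab share among rerandomized subjects, and on reaching about 40 rerandomized. Other visits and the PASI endpoints move the same way only as far as they track Week 60 response. No hypothesis test is affected. It should be corrected because this is the default population for long-term efficacy, and the adjacent row already shows the right approach.

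**What to change.** - **Redefine the population.** Include all subjects randomized to ixekizumab at Week 0, and exclude only records after the Week 60 rerandomization for those assigned placebo. State that the Week 60 assessment made at rerandomization counts as Period 3 data, and that the excluded records are out of the denominator and not missing values to be set to nonresponse under SAP 6.3.1.
- **Specify Period 4.** Record-level exclusion alone leaves all EU nonresponders but about half of EU responders after Week 60. The rate would then step from 80.0% to between 77.3% and 78.4% with no change in any subject. Either report EU rerandomized responders and the open-label extension in separate rows, or give EU responders kept on ixekizumab a weight of 2. With equal numbers kept and dropped, the weighted rate is (88 - k + k)/(110 - k + k) = 80.0%. This holds in expectation under 1:1, not exactly in a given sample. Separate rows are simpler.
- **Reconcile Table RHCD.6.4 with SAP 6.11.4** for Weeks 24 and 48. Under the corrected definition both give the full Week 0 ixekizumab arm.

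The cost is SAP wording, a record-level flag in place of a subject-level flag, and an extra row or weight in the Period 4 tables. No data collection changes. SAP Version 3 was approved after the primary database lock, at which Period 2 is unblinded, and the change raises the ixekizumab rate. It should therefore be a dated amendment with its reason stated, and showing the rate under the existing definition alongside would make the effect visible.
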